7.9.1.1.4 Analysis Methods

VenousTSQe and VenousTSQs consist of 8 and 11 items, respectively, with each item having the possibility to be scored from 0-6. The scores will be collected from eCRFs at 30 days.

The VenousTSQe score is calculated as:

Item 1 (from the VenousTSQs) + Item 2 + Item 4 + Item 5b + Item 6b + Item 7

Items 1, 3, and 8 from the VenousTSQe are not used.

Since the VenousTSQe score is the sum of 6 items, it can range from 0 to 36.

The Venous TSQs score is calculated as:

Item 1 + Item 2 + Item 4b + Item 6 + Item 7b + Item 9

Items 3, 5, 8, 10 and 11 are not used.

Since the VenousTSQs is the sum of 6 items, it can range from 0 to 36.

Scoring Notes

Some items included in the scores are skipped when they are not applicable, based on a previous question. For example, consider 5a and 5b in the VenousTSQe

5a asks: "Immediately after the procedure, did you wear compression stockings or bandages?" If the response to 5a is "no", 5b is skipped. 5b asks "How bothered were you by wearing compression stockings / bandages?", so it doesn't apply if no stockings / bandages were worn. In these cases, when an item in the score is skipped because of a response to the prior, related question, it will be scored as 6. For item 5b, 6 indicates "not bothered at all", which is sensible, since a person cannot be bothered by stockings that are not worn.

If the follow-up question is supposed to be skipped, but is not, the follow-up response will be used only if it is consistent with the prior, related question. If 5a is marked "no" (indicating that stockings were not worn), and 5b is not skipped, then:

- If 5b = 5 or 5b = 6, 5b will be used to calculate the score.
- If 5b < 5, then the responses are inconsistent, and 5b will be considered missing.

If a prior question is marked "yes", but the follow-up question is left blank, then the item will be considered missing:

- If 5a is marked "yes", but 5b is missing, then 5b will be considered missing.

Calculating the Score When Items are Missing

The VenousTSQe and VenousTSQs scores are missing when any of the included items is missing.

Hypothesis Test of the TSQ

(Shapiro-Wilk test) Normality on the outcomes of primary endpoints of PROM scores and % of target vein length successfully treated will be checked in each treatment arm first.

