7.9.1.1.6 Sensitivity and Missing Data Analysis

It is recommended to perform an additional scoring of the TSQe that does not include Item 5, i.e. the Compression stockings question.

To account for missing data in the primary endpoint evaluation, two forms of imputation will be performed. For patients that have no baseline information collected, they will be assigned the average value of the TSQ in the control arm. For patients with a baseline visit and baseline information collected, multiple imputation will be performed as a sensitivity analysis. Subjects who do not obtain their VenousTSQe at 30 days, VenousTSQs at 30 days or the percentage of target vein treated at procedure will have these measurements imputed using PROC MI in SAS. The covariates to be used in the imputation model are age, gender, race, diabetes, CEAP classification, Historical Superficial and Deep Venous Treatment, Family History of Chronic Venous Disease, VCSS at baseline, 7 days and 30 days, Length of clinically relevant superficial truncal disease in target vein and treatment arms. Ten imputed data sets will be generated using regression method (REG option in PROC MI). The overall PROM scores for VenousTSQe and VenousTSQs and % target vein treated success and their standard errors will be generated for each of ten imputed data sets. PROC MIANALYZE in SAS will be used to summarize the overall treatment difference, standard error, and two-sided 95% confidence interval.

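### The sensitivity imputation for the TSQ primaries does not use the items a subject has answered, although one missing item makes the whole score missing

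*SAP*

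**What the plan says.** **Scores.** SAP 7.9.1.1.4 defines both TSQ primaries as six-item sums: "Since the VenousTSQe score is the sum of 6 items, it can range from 0 to 36", and "Since the VenousTSQs is the sum of 6 items, it can range from 0 to 36". The TSQe sum is "Item 1 (from the VenousTSQs) + Item 2 + Item 4 + Item 5b + Item 6b + Item 7", so item 1 of the TSQs enters both scores.

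**Missing items.** The same section states: "The VenousTSQe and VenousTSQs scores are missing when any of the included items is missing". There is no prorating. The AVVQ, a secondary endpoint, does have a proration rule (SAP 7.9.1.7, endpoint 4).

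**Gated items.** When the gate question is answered *no* and the follow-up is left blank, the follow-up scores 6. If it is answered anyway, a 5 or 6 is kept, but "If 5b < 5, then the responses are inconsistent, and 5b will be considered missing". A blank follow-up after *yes* is also missing. Items 5a/5b are given as an example; by the questionnaires in Protocol Appendix A, the rule reaches TSQe 5b and 6b and TSQs 4b among the scored items.

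**Analysis.** SAP 7.9.1.1.5 bases the primary analysis on ITT subjects with available data. SAP 7.9.1.1.6 then gives subjects without baseline information the control-arm mean. For the others it imputes the TSQe, the TSQs and the percentage of vein treated in ten data sets by PROC MI regression. The list of predictors opens "The covariates to be used in the imputation model are age, gender, race, diabetes, CEAP classification", goes on to prior venous treatment and family history, and ends with "VCSS at baseline, 7 days and 30 days, Length of clinically relevant superficial truncal disease in target vein and treatment arms".

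**The concern.** A subject who answers five of six items has told the trial nearly everything about the total. The plan drops that subject from the primary test. In the sensitivity analysis it then treats the total as wholly unknown, to be predicted from background variables and clinical severity.

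SAP 7.4 says the imputation is there to show how much missing data could matter. If the subjects with incomplete forms are more (or less) satisfied than the rest of their arm, their answered items show it. An imputation that does not see those items will tend to agree with the complete-case result and so give false reassurance. This concerns two primary endpoints in both randomized studies.

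**Working it through.** **1. The plan's own figure.** Inputs from SAP 6.1.1: difference 0.5 per item, SD 1 per item, two-sided alpha 0.0167, 1:1 allocation, 90% power, 7% attrition. On a six-item score that is a difference of 3 with SD 6. A noncentral t calculation gives 110 per arm with power 0.902, and 220/0.93 = 236.6, so 237. The stated 220 evaluable and 237 total reproduce. The SAP does not say whether the 7% covers forms returned with a missing item.

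**2. How many scores could be lost.** The documents give no item-missing rate. Assume each item is missing independently with probability m among returned forms. Then P(score missing) = 1 − (1 − m)^6.

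| m (assumed) | Scores lost | Power, N = 237 | Power, N = 264 (ETA study) |
|---|---|---|---|
| 0 | 0 | 0.902 | 0.933 |
| 0.5% | 3.0% | 0.892 | 0.925 |
| 1% | 5.9% | 0.882 | 0.917 |
| 2% | 11.4% | 0.859 | 0.898 |

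Power is by noncentral t at alpha 0.0167 on N × 0.93 × (1 − m)^6 subjects. A blank follow-up after *no* scores 6, so gated items are not always at risk and the losses shown are somewhat high for a given m.

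**3. What the answered items carry.** Assume equal item variances and a common inter-item correlation r. The variance of the total (unit item variance) is 6 + 30r. The missing item's variance given the other five is 1 − 5r²/(1 + 4r). So

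R² = 1 − [1 − 5r²/(1 + 4r)] / (6 + 30r).

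- r = 0.2: 5(0.04)/1.8 = 0.111; (1 − 0.111)/12 = 0.074; R² = 0.926.
- r = 0.6: 5(0.36)/3.4 = 0.529; (1 − 0.529)/24 = 0.020; R² = 0.980.

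**4. What the other form carries.** With the one shared item and the same r across forms, the correlation of the two totals is (1 + 35r)/(6 + 30r). At r = 0.2 this is 8/12 = 0.667, R² = 0.44. At r = 0.6 it is 22/24 = 0.917, R² = 0.84. Weaker cross-form correlation lowers this. If the shared item is the one missing, both scores are lost and the other total cannot help.

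**5. Effect on the estimate.** Simulation: 110 per arm, true difference 3, SD 6, r = 0.4, background covariates with R² 0.10 (assumed), about 10% of scores lost through one item, ten imputations, 2,000 replicates.

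| | Full data | Complete cases | MI, listed type of covariates | MI with answered items |
|---|---|---|---|---|
| SE, loss at random | 0.807 | 0.851 | 0.851 | 0.809 |
| Mean estimate, low-scoring controls skip more (log-odds 0.5 per SD) | 3 (truth) | 2.68 | 2.71 | 3.02 |

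The planned type of imputation recovers essentially none of the lost precision and follows the complete-case bias. Adding the answered items removes both problems. The bias would change sign if the selection ran the other way.

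**6. The contradiction rule alone.** If 10% of those answering *no* to 5a still answer 5b (assumed), about 4% of an arm with 90% *no* lose their score, against about 1.5% of an arm with 30% *no*. Over a range of such assumptions the direct bias is 0.02 to 0.13 points on a 3-point difference, which is small.

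**The case against.** Several stronger readings are tempting, and the documents do not support them.

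- **That this imputation is the only check on missing primary data.** SAP 7.9.1.1.6 also has the control-arm mean for subjects without baseline information. It also recommends rescoring the TSQe without item 5, which removes the 5a/5b contradiction altogether. That rescoring does not reach 6b, 4b or ordinary blanks, and the control-arm mean uses no answers.
- **That the other TSQ form is ignored.** The SAP does not say whether the outcomes are imputed separately or in one PROC MI run. In a joint run one total could inform the other. This is unstated rather than excluded, and the answered items would still go unused.
- **That such subjects are replaced by near-average values.** Regression imputation draws around a prediction that includes arm, with residual variation. Only the expectation is near the arm's average.
- **That the scoring rule should change so that every gated *no* scores 6.** A subject who ticks *no* and then circles 0 would receive the best score, which hides an expressed dissatisfaction. The SAP version history also says that scoring follows final recommendations, which are not in the documents.

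Other points stand. All item-missing rates and correlations here are assumed. Data queries (Protocol 16.5) may keep item loss low. The ETA study enrols 264 against the 237 needed, so its power loss is slight. A wholly missing questionnaire has no answered items, and the imputation decides no hypothesis.

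**Conclusion.** The point holds for partly completed forms. The scoring rule discards a total when five of six components are known, and the imputation model as listed discards those five as well. Their value is high under any plausible correlation (93% to 98% of the total's variance for r from 0.2 to 0.6), whereas the listed covariates recovered almost nothing in the simulation at an assumed R² of 0.10.

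How much this matters in the trial depends on the item-missing rate, which the documents do not give: about 3% to 11% of returned forms at 0.5% to 2% per item. The shift from 3 to about 2.7 needs roughly 10% loss and selection in one arm, and nothing in the documents shows that either will occur. The weakness lies in the imputation model; the contradiction rule on its own adds little bias.

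**What to change.** In SAP 7.9.1.1.6:

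1. Impute the TSQ items by fully conditional specification, by arm, and sum them afterwards. Apply the present scoring first, so that valid skips are already 6. The two scores involve 6 + 6 − 1 = 11 distinct items. The stripping study has 108/2 = 54 subjects per arm, so a shorter covariate list, or arm as a predictor, may be needed there.
2. If item-level imputation is not wanted, at least add the answered items and the other TSQ form to the model, and say that the outcomes are imputed jointly.
3. Optionally add NRS pain at 7 and 30 days (Protocol 10.5) and the 6-month TSQs (Protocol Table 6) as auxiliary variables. Only these help when both forms are wholly missing.
4. Report, by arm, how many scores are missing because the form was not returned, an item was blank or answers were contradictory, and state whether the 7% attrition includes incomplete forms.

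Leave the scoring in SAP 7.9.1.1.4 as it is. Scoring a contradictory follow-up as 6 may be shown as an added sensitivity analysis only.

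The cost is SAP wording and a little more programming, on data already collected. The primary analysis and the sample size do not change.

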7.9.1.2 Analysis of Key Secondary Endpoints

7.9.1.2.1 Hypothesis

For key secondary endpoint of return to work, the following hypothesis will be tested:

$$H_0: S_A(t) = S_C(t)$$

$$H_a: S_A(t) \neq S_C(t)$$

Where $S_A(t)$ and $S_C(t)$ are the survival functions for freedom from return to work for the VenaSeal™ system arm and ETA or surgical stripping arm, respectively.

For the other key secondary endpoint of primary target vein closure rate at 6 months, the following hypothesis will be tested:

$$H_0: S_A(t) \leq S_C(t) - 10\%$$

$$H_a: S_A(t) > S_C(t) - 10\%$$

Where $t = 6$ months, and $S_A(t)$ and $S_C(t)$ are the survival functions for freedom from vessel re-opening at 6 months in the VenaSeal™ system arm and the ETA or surgical stripping arm, respectively and -10% is the non-inferiority margin.

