Post-index procedure, DUS evaluation is required to assess target vein (including primary target vein) closure after VenaSeal™ system or ETA treatment and absence of refluxing vein or residual vein after surgical stripping. DUS is also used for thrombus assessment. This DUS assessment will also be performed at 7 days, 30 days, 6, 12, 24, 36, 48 and 60 months. This DUS assessment could be completed on the day of the follow-up visit or anytime during the follow-up visit window, as applicable to the site's standard scheduling process.

Patient-Reported Symptoms

Subjects will be asked to report symptoms related to their target limb: pain, aching, itching, burning, sensitivity, heaviness and swelling, and asked to identify their dominant symptom from this list. This will be assessed at baseline and at follow-up visits through 12 months. These questions must be completed by the subject and a translation will be available in each of the applicable languages; however, designated site staff may verbally read the symptom list to the patient.

Venous Treatment Satisfaction Questionnaire (VenousTSQ)

The two components of the VenousTSQ are evaluated as two separate primary endpoints in this study. The questionnaire needs to be completed either by the subject or by a delegated person who asks the questions to the subject and completes the questionnaire on behalf of the subject. This should be the first subject-reported assessment at all study visits when administered.

The Venous Treatment Satisfaction Questionnaire (VenousTSQ) is a new Patient Reported Outcome Measure (PROM). Via a qualitative design approach involving patient interviews and clinical expert reviews, the process resulted in an independently developed tool for venous patients. The tool consists of two components, the peri-procedural early component of treatment satisfaction which will be measured at 30 days post index-procedure (VenousTSQe), and the longer-term status component of treatment satisfaction which can be measured at 30 days, 6 and 12 months (VenousTSQs). Questions focus on topics relevant for patients with varicose veins who have undergone a venous treatment and include items on treatment satisfaction/dissatisfaction, symptoms such as pain, and outcome satisfaction/dissatisfaction.

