10.11. Unscheduled Visits

A visit outside of the study follow-up schedule will be reported as unscheduled study visit if it was conducted for the evaluation of an AE per the AE reporting requirements in this study. In addition to any applicable AE treatment or diagnostic testing, the following additional assessments may be completed, per the treating physician's discretion (limb specific assessments are of the target limb only):

1. Required: AE assessment
2. CEAP classification
3. rVCSS
4. DUS.

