No Procedure treatment outcome (CEAP 2-5)	Subject is randomized (considered enrolled) but withdraws from the study after randomization without any attempt to conduct the procedure (e.g. COVID-19 exclusion, subject withdrawal, etc.).
Per-Protocol (PP) (CEAP 2-6)	The ITT population excluding subjects that are not treated with the assigned treatment modality and/or have not met the inclusion/exclusion criteria.
Phlebectomy	Surgical procedure to remove small varicose veins through a series of small (1-3 cm) incisions in the leg along the GSV and its tributaries.
Phlebitis	Inflammation of a vein, the grading of the phlebitis are as follows and subject may have more than one grading: P1: Inflammation of truncal or epifascial vein post-treatment, with palpable and/or non-palpable (Superficial thrombophlebitis) areas. Located within the treatment zone. It is caused due to Damage to treated vein by prescribed treatment with and without thrombus. P2: Superficial thrombophlebitis in residual varicosities/tributaries. Located outside of treatment zone. It is caused due to thrombosis of draining varices or tributaries secondary to closure of truncal vein P3: Inflammation of cutaneous and subcutaneous tissue. Located within or outside of treatment zone and adjacent tissues. It is caused due to tissue reaction to treatment or hypersensitivity.
Point of Enrollment (CEAP 2-5)	Subjects will be considered enrolled from the moment of randomization.
Point of Enrollment (CEAP 6)	Subjects will be considered enrolled from the moment the first component of the VenaSeal™ delivery system enters the body.

Medtronic Business Restricted

CONFIDENTIAL

VENASEAL SPECTRUM Clinical Investigation Plan

MDT18034

Version 5.0

Page 150 of 164

Medtronic

Pre-Screen Failure	Patients that were identified for screening (consenting in the study) but were not consented in the study
Pre-Screening	The process of identifying patients for potential inclusion in the study, prior to obtaining informed consent from the patient.
Primary Target Vein	The primary target vein should be the saphenous vein (GSV, SSV, accessory saphenous veins) which at the investigator's discretion is most likely responsible for the greatest portion of the patient's symptoms or pathology. This vein will be treated first.
Reintervention	Retreatment of any segment of the target vein in the target limb previously treated as part of the study at the index procedure.

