7.8	Interim Analyses.....	23
7.9	Evaluation of Objectives	23
7.10	Safety Evaluation.....	52
7.11	Health Outcomes Analyses	53
7.12	Changes to Planned Analysis.....	53
8.	Validation Requirements.....	54

9. References	54
10. Statistical Appendices.....	54

1. Version History

Version	Summary of Changes	Author(s)/Title
1.0	
 Not Applicable, New Document 	[name], Principal Statistician
2.0	
 Update to note that elimination of truncal reflux will be summarized without hypothesis testing for the VenaSeal vs. Surgical Stripping Study, due to halted enrollment in sections 4.1, 7.5 and 7.9. Updated study design consistent with CIP changes in sections 5.1, 5.2, 6.2 and 7.9.3 (halting of Venaseal vs. Surgical Stripping study enrollment and reducing follow-up to 12 months and reduction in sample size of the VLU study) Add note on handling of VenaSeal vs. Surgical Stripping study data collected beyond 12 months in section 7.1.1 Added the scoring algorithm for the VenousTSQe and VenousTSQs in section 7.9.1.1.4 Added test for superiority in non-inferiority is met in section 7.9.1.2.3 Document updated using new template. 	[name], Principal Statistician
3.0	
 Re-organized the document so that each study endpoint is enumerated and the corresponding hypothesis, endpoint definition, analysis methods and analysis population are provided Return-to-work endpoints, return-to-normal activities, anatomic closure endpoints all revised use a time-to-first-event analysis to allow for censoring and incorporation of unscheduled follow-up visits Reintervention and healthcare utilization endpoints are revised to use a rate-based calculation to allow for potential recurrent events and differences in follow-up time Updated scoring of the VenousTSQe and VenousTSQs based on the final recommendations 	[name], Distinguished Statistician

2. List of Abbreviations and Definitions of Terms

Abbreviation	Definition
AE	Adverse Event

Abbreviation	Definition
AVVQ	Aberdeen Varicose Vein Questionnaire
CEAP	Clinical, Etiological, Anatomical, and Pathophysiological Classification
CIP	Clinical Investigation Plan
CRF	Case Report Form
DUS	Duplex Ultrasound
DVT	Deep Vein Thrombosis
EGIT	Endovenous glue induced thrombosis
EHIT	Endovenous heat induced thrombosis
EQ-5D	EuroQoL 5 Dimensions Standardized Quality of Life Survey
EVLA	Endovenous Laser Ablation
ETA	Endovenous Thermal Ablation

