7.9.1.2.2 Endpoint Definition

Return to work is defined as the time in days patients need following a procedure to return to work. Employment status will be captured for all patients. Only patients who have an active employment status (employed or independent worker, including stay at home parents) will be included in the analysis for return-to-work time. Information will be captured on the category of occupation to be able to distinguish between physical and sedentary work. Patients will be censored at the time of study exit.

The other key secondary endpoint to be assessed is the primary target vein closure rate after index treatment. The primary target vein should be the saphenous vein (GSV, SSV, accessory saphenous veins) which at the investigator's discretion is most likely responsible for the greatest portion of the patient's symptoms or pathology. This vein will be treated first.

For subjects treated with the VenaSeal™ system or ETA, anatomic closure of the primary target vein is defined as Doppler ultrasound (DUS) showing primary target vein closure along the entire treated vein segment with no discrete segments of patency exceeding 5 cm. Any areas with >5 cm patency will be measured, and information will be collected on the location of the patency, length of the patency (cm), diameter of the patency (mm), the presence of flow (Y/N), the presence of reflux (Y/N), and the presence of thrombus (Y/N). For subjects treated with surgical stripping, anatomic closure of the primary target vein is defined as the absence of clinically significant refluxing truncal vein incompetency and no discrete segments of patency exceeding 5 cm in the primary target vein. Any areas with vein remnants will be measured and information will be collected on the location of the remnant, length of the remnant (cm), the presence of flow (Y/N), the presence of reflux (Y/N), and the presence of thrombus (Y/N). Lack of anatomic closure on the date of the index procedure will not be considered relevant to this endpoint, since some treatments may not achieve closure immediately.

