7.9.1.2.4 Analysis Methods

For the return to work endpoint, a Kaplan-Meier survival estimator will be used to estimate the survival functions for both the VenaSeal™ and the control arm (i.e., ETA or Surgical Stripping). Day zero is the date of the index procedure. The censoring time is the time to study exit, the later of either the last contact date or the discontinuation date, or the time point for analysis, whichever comes first. A cumulative incidence figure will be produced to compare the two treatments. A log-rank test will be used to test whether the survival distributions differ between the treatment groups. If a patient is reported to have returned to work, but the date of return is unknown, the return date will be imputed from the date of the follow-up visit. For those who have returned to work, the median, Q1, Q3, minimum, and maximum will summarize the number of days to return to work, as well as the number who have not returned to work in each treatment arm.

The treatment effect for primary target vein closure at 6 months, one of the key secondary endpoints, is the difference in the survival curves at time t for each randomized study. A Kaplan-Meier survival estimator will be used to estimate each curve. Day zero is the date of the index procedure. The censoring time is the time to last study visit (scheduled or unscheduled), the time point for analysis, or time to exit, whichever comes first. The non-inferiority test for treatment (VenaSeal) versus control (ETA or Surgical Stripping) will be performed using the test statistic proposed in da Silva, Logan and Klein (2009)³. The Z test statistic will calculate $S_A(t) - S_C(t) + 0.10$ for the numerator where t is at 6 months and the square root of the sum of the Greenwood's variance estimators for each of $S_A(t)$ and $S_C(t)$ in the denominator.

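### Reintervention is not a closure event, so a primary target vein re-treated before any study ultrasound records its re-opening counts as closed at 6 months

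*SAP*

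**What the plan says.** **Event.** SAP 7.9.1.2.1 tests non-inferiority, with a 10-point margin, on the "survival functions for freedom from vessel re-opening at 6 months". SAP 7.9.1.2.2 defines closure by DUS for VenaSeal and ETA (no patent segment over 5 cm) and by a reflux-and-patency criterion for stripping. Only one finding is set aside: "Lack of anatomic closure on the date of the index procedure will not be considered relevant to this endpoint".

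**First event.** The SAP version history (version 3.0) has "anatomic closure endpoints all revised use a time-to-first-event analysis to allow for censoring and incorporation of unscheduled follow-up visits".

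**Censoring.** SAP 7.9.1.2.4: "The censoring time is the time to last study visit (scheduled or unscheduled"), the analysis time point or exit, whichever comes first.

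**Reintervention.** CIP Appendix B defines it as "Retreatment of any segment of the target vein in the target limb previously treated as part of the study at the index procedure". SAP 7.9.1.4 analyses it as two separate secondary endpoints (items 4 and 5). The closure sections do not mention it.

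**When the vein is scanned.** CIP 10.5: "This DUS assessment will also be performed at 7 days, 30 days, 6, 12, 24, 36, 48 and 60 months". Under CIP 10.11 an extra visit is "reported as unscheduled study visit if it was conducted for the evaluation of an AE", and DUS there is at the physician's discretion. CIP 6.1 and SAP 5.2 state that routine-care visits for adjunctive procedures from 3 months are not study visits. CIP 10.10 lists only adjunctive therapy and AE assessment for them.

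**The concern.** The endpoint is meant to show whether the index treatment closed the vein and kept it closed to 6 months. It depends wholly on a study DUS seeing the re-opening. Where the re-opening is found and corrected between scans, the only trace may be a reintervention record, which the closure analysis does not use. The next study DUS then shows a vein closed by a second procedure.

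This is one of two formally tested key secondary endpoints, and SAP 7.9.1.2.3 adds a superiority test if non-inferiority is met. In a non-inferiority comparison, losing the same share of failures from both arms shrinks a true difference and makes the claim easier. The studies are also unblinded (CIP 6), so the decision to re-treat between scans may differ by arm.

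**Working it through.** **1. The plan's own figure.** Inputs from SAP 6.1.2: closure 95% (VenaSeal) and 95.4% (ETA), margin 10 points, one-sided 0.0167, Farrington-Manning test, 1:1, 10% attrition. With the variance constrained to the null, 119 per arm gives 80.3% power. Then 238 / 0.9 = 264.4, against 264 stated. The figure reproduces.

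**2. Length of the unscanned interval** (CIP 10.2, Table 8).
- Target to target: 182 − 30 = 152 days.
- Shortest within the windows: 154 − 37 = 117 days.
- Longest within the windows: 210 − 23 = 187 days.

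**3. Three cases under the SAP's rules.** Take ten subjects, nine closed throughout to day 182. The tenth re-opens at day 100, is re-treated, and is closed on the day-182 DUS.

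| What the study data hold for the tenth subject | SAP result | Closure at 6 months |
|---|---|---|
| Study DUS at day 100 shows over 5 cm patent | Event at day 100 | 9/10 = 0.90 |
| No study DUS before re-treatment | No event, censored at day 182 | 10/10 = 1.00 |
| Same, with reintervention counted as loss of closure | Event at reintervention date | 9/10 = 0.90 |

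The first row is handled correctly. The second is the gap.

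**4. Illustrated size.** Assumptions:
- 119 evaluable per arm.
- True failure 4.6% (ETA) and 14.6% (VenaSeal), so the deficit is exactly 10 points.
- A share h of failures is hidden in both arms.
- With no other censoring, the SAP's statistic reduces to Z = (pA − pC + 0.10) / √[pA(1−pA)/119 + pC(1−pC)/119].

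Observed closure is pA = 1 − 0.146(1−h) and pC = 1 − 0.046(1−h), so the apparent deficit is 10(1−h) points. Summing exact binomial probabilities over all outcomes with Z above the one-sided 0.0167 critical value gives:

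| h | Apparent deficit | P(declare non-inferiority) |
|---|---|---|
| 0 | 10.0 points | 2.5% |
| 5% | 9.5 points | 3.4% |
| 10% | 9.0 points | 4.7% |
| 20% | 8.0 points | 8.7% |

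The first row exceeds the nominal 1.67% because of the unpooled variance, not because of reintervention. Only the rise from 2.5% belongs to this point. At one-sided 0.05, the most lenient level in SAP 7.5, the values for h = 0 and 20% are 6.0% and 16.5%.

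**5. At the planning rates.** With 95% against 95.4%, hiding 20% in both arms moves the expected difference only from 0.4 to 0.4 × 0.8 = 0.32 points. The distortion matters when VenaSeal is truly worse.

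**The case against.** A reader might infer that any vein that re-opens and is re-treated before 6 months is counted as a success, so that the endpoint credits the second procedure to the device. The documents do not support that. Re-opening is the event, only the first event counts, and the only non-closure set aside is that on the index date. The CIP's wording of the endpoint (5.2.2), a DUS finding at 6 months, could be read that way alone, but it is not the analysis the SAP tests.

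What remains needs a chain of conditions: no failing DUS at Day 7 or Day 30, later re-opening, discovery without a recorded study DUS, and re-treatment before the 6-month scan. The CIP narrows this further. All target-limb AEs are reportable (12.3), so a symptomatic re-opening may generate an unscheduled study visit. Table 6 lists DUS at such visits, and CIP 10.5 asks for rVCSS there before a target-vein intervention. This limits how often the gap can occur. It does not close it, because DUS at those visits is discretionary and routine-care visits are not study visits.

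It is also fair that the hidden shares are assumed. They apply to all failures, including those that the Day 7 and Day 30 scans would catch, so the share among later failures would have to be higher. The direction depends on hiding in both arms: if only control failures were hidden, the control arm would look better and non-inferiority would be harder to declare.

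The strongest objection is to the remedy. Reintervention covers any treated segment with no patency threshold, so counting it makes an anatomic endpoint a composite that includes an unblinded clinical decision. That stands, and is why the DUS-only analysis should be kept.

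**Conclusion.** The point holds as a gap in the endpoint definition. Followed exactly, the SAP counts as closed a primary target vein that was re-treated between Day 30 and the 6-month scan with no study DUS recording the re-opening. Re-openings that a study DUS does record are handled correctly.

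The documents give no rate of such re-treatment, so no single corrected result can be stated. For 5% to 20% of failures hidden in both arms, false non-inferiority at the margin rises from 2.5% to between 3.4% and 8.7%. That range rests on 119 per arm, equal hidden shares, the unpooled Z and one-sided 0.0167. At the planning rates the effect on the expected difference is negligible. The change is worth making because the endpoint is formally tested and the rule is simple to state before analysis.

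**What to change.** In SAP 7.9.1.2.2, 7.9.1.4 items 1 and 2, and 7.9.2.3 items 4 and 5:
- Define loss of closure as the earlier of (a) the first post-index DUS that fails the closure criterion for that arm and (b) the first reintervention on that vein, dated at the reintervention.
- Apply this identically in all arms, and disregard later DUS findings for that vein.
- State how a reattempt to complete the index procedure (CIP 9.2) is treated, since the CIP counts it as part of the assigned treatment.
- Report the present DUS-only definition as a sensitivity analysis.
- Keep reintervention rate and time to reintervention as separate endpoints.

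**Cost.** One definition and one programming rule, with no new visits. Reintervention dates are already needed for the time-to-reintervention endpoint, though each must be linked to a specific vein. The sponsor should judge under SAP 7.12 whether the change alters a principal feature of the CIP.

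**Downside.** Closure rates become slightly less favourable. A discretionary, unblinded re-treatment of a segment under the 5 cm threshold would count as a failure, which the DUS-only analysis would show. Power falls if such cases are common. Assuming 1%, 2% or 3% of veins in both arms become additional failures, power against ETA at 119 per arm falls from 80.3% to 75.1%, 70.4% or 66.1% on the sizing test. On the unpooled Z it falls from 90.9% to 85.1%, 79.2% or 73.7%.
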